2.6 Site merging

Data from all sites in this study will be merged together for analysis and statistical inference.

3 Statistical analysis method

3.1 Basic information of subjects

3.1.1 Disposition of subjects

For all and each site(s), all subjects who signed the Informed Consent Form (ICF) will be summarized for screen success and screen failure, and the reasons for screen failure will also be summarized. The number and percentage of subjects who completed the study and those of subjects who discontinued the study will be summarized based on subjects with screen success. The reasons for study discontinuation will be presented in a table. In addition, the number and percentage of subjects who entered the roll-in analysis set (RI AS), the full analysis set (FAS), the per protocol set (PPS), the safety set (SS), the safety analysis set as treated (SS AT), and the roll-in analysis set as treated (RI AT), as well as the follow-up rate of patients will be summarized.

The information on subject screening and study completion will be tabulated based on all subjects who signed the ICF.

3.1.2 Protocol deviations

Before database lock, protocol deviations will be reviewed and assessed by the investigators and the sponsor and classified as major or minor. Major protocol deviations will be tabulated by type based on the enrolled patient set.

All protocol deviations will be tabulated, and sorted by type of protocol deviation, site, subject ID, and date of deviation.

3.1.3 Demographics and baseline characteristics

Subject demographics and baseline characteristics will be summarized descriptively based on the RI AS, FAS, and SS.

Demographics:

- Age (years)
- Age: < 45 years, [45, 65 years) , \geq 65 years
- Gender (M, F)

Baseline characteristics:

- Height (cm)
- Weight (kg)
- BMI (kg/m²)
- Pulse (bpm)
- Blood pressure systolic/blood pressure diastolic (mmHg)
- mRS score (0, 1, 2, 3, 4, 5, 6)
- CHADS₂ score (points)
- CHADS₂ score (points) (0, 1, 2, 3, \geq 4)
- CHA₂DS₂-VASc score (points)
- CHA₂DS₂-VASc score (points) (0, 1, 2, 3, \geq 4)
- Pre-procedure anticoagulant therapy (Yes, No)
- Pre-procedure left atrial thrombus detection method
- Whether a left atrial thrombus is found (Yes, No)

3.1.4 Cardiovascular medical history

Cardiovascular medical history of subjects will be summarized descriptively based on RI AS, FAS, and SS. Medical history categories not prespecified will be coded using the Medical Dictionary for Regulatory Activities (MedDRA, V25.1 or higher) and summarized by number and percentage according to the System Organ Class (SOC). The denominator is the number of subjects in the analysis set.

The cardiovascular medical history will be summarized by the presence of any known cardiovascular medical history with specific details, the presence of any confirmed embolism and specific type of occurrence, the presence of deep vein thrombosis, and the presence of any cerebrovascular event which is not secondary to embolism.

3.1.5 Other medical history

Other medical history will be summarized descriptively based on RI AS, FAS, and SS. Other medical history includes diabetes mellitus history (type I, type II), obstructive sleep apnea (OSA), abnormal blood routine test results, abnormal

liver function and abnormal renal function. The number and percentage of subjects with other medical history will be summarized according to the specific instructions in eCRF.

3.1.6 Atrial fibrillation history

AF history of subjects will be summarized descriptively based on RI AS, FAS, and SS. The summary will be performed as follows:

- Duration of symptomatic PAF
Duration of symptomatic PAF (months) = (date of index ablation procedure - date of first symptomatic PAF episode) / 30.4375, wherein $30.4375 = (365*3+366)/(4*12)$.
- In the past 12 months, did the subject experience an episode of PAF
- Methods of identifying AF episodes
- Symptoms related to PAF episodes
- Number of episodes of PAF in the past 12 months
- Average duration of episodes in the past 12 months
- Average frequency of episodes in the past 12 months
- Arrhythmia type other than PAF
- Presence of ablation procedure history
- Number of previous ablation procedures, for subjects with arrhythmias treated by ablation in previous procedures
- Types of arrhythmias treated by ablation in previous procedures
- Time since last ablation (months) = (date of index ablation procedure - date of last ablation procedure) / 30.4375, wherein $30.4375 = (365*3+366)/(4*12)$.
- Technology used in the last ablation procedure

3.1.7 Assessment of left atrium (LA), left ventricular ejection fraction (LVEF), and pericardial effusion

Findings for baseline LA, LVEF and pericardial effusion will be summarized descriptively based on RI AS, FAS, and SS.

- Method of measurement
- LVEF (%)
- Left atrial diameter (mm)

- Left atrial volume (mL)
- Is any valvular regurgitation observed
 - If yes, valve type
 - Severity of regurgitation
- Pericardial fluid assessment
- Whether there is abnormal heart wall motion

3.1.8 Previous/concomitant therapy

Therapeutic classes will be pre-specified and coded using the World Health Organization Drug Dictionary (WHODRUG, September 1, Version 2022 or higher) and the number and percentage will be calculated by Anatomical Therapeutic Class (ATC) and/or preferred name.

3.1.8.1 AAD medication history

Antiarrhythmic drug (AAD) medication history of subjects will be summarized descriptively based on RI AS, FAS, and SS.

- Previously failed Class I/Class III AADs (Yes, No)
- Reason for failure
- Contraindicated for Class I/Class III AADs (Yes, No)
- Reason for contraindication
- Class I/III AAD treatment failures or contraindications (Yes, No)
- Classes and names of all failed AADs used for atrial fibrillation treatment
- Number of types of failed Class I/III AADs used for atrial fibrillation treatment (continuous variable)
- Number of types of failed Class I/III AADs used for atrial fibrillation treatment (0, 1, 2, 3, 4, ≥ 5)
- Beta blocker
- Calcium channel blockers

Details of prior Class I/III AAD medication such as the reason for failure, the reason for contraindication, and the historical maximum dose will be tabulated by subject.

3.1.8.2 Other prior/concomitant medications

Other prior/concomitant medications for subjects will be separately summarized descriptively based on RI AS, FAS, and SS. The types of medication and reasons

for medication will be summarized. Meanwhile, medications will be coded using World Health Organization Drug Dictionary (WHODRUG, September 1, Version 2022 or higher), and the number and percentage will be calculated by Anatomic Therapeutic Class (ATC) second level and preferred name (PN).

Other prior medications refer to non-investigational medications that are discontinued before the index ablation procedure.

Concomitant medications refer to non-investigational medications which meet one of the following conditions:

[figure not shown]
- (1) All medications start before index ablation procedure and continue after index ablation procedure.
- (2) All medications start on or after index ablation procedure.

CCI

Table 2

CCI

3.1.9 Intra-procedure patient information for index ablation procedure

Index ablation procedure related information will be summarized based on RI AT, FAS, and SS AT.

- Anesthesia type
- Anesthetics
- Using ICE to assess the presence of left atrial thrombus (Yes/No)
 - Presence of left atrial thrombus (Yes/No)

- Is heparin administered (Yes/No)
- Transseptal access
- Which imaging modality is used to guide transseptal puncture
- Sheath type
- Is the Multi-electrode Circular IRE Catheter inserted
- Is a left atrial map acquired prior to PFA
 - If yes, catheter type/imaging method
- PV anatomy
- Is a left atrial voltage map acquired prior to PFA
 - If yes, total mapping duration (min)
- Is PFA applied via the investigational catheter (Yes/No)
- Ablation target
- Total ablation time (min) (defined as the last application time – the first application time)
- Total valid PFA application time (sec)
- Number of valid PFA applications (total, used to ablate PVs, used to ablate non-PVs)
- Study catheter LA dwell time (min) (defined as the time of catheter withdrawal from LA - the time of first catheter insertion in LA)
- Total procedure time (min)
- Total duration of fluoroscopy at end of procedure (min)
- Is a Foley catheter placed
- Fluid delivered via the investigational catheter (ml)
- Fluid delivered intravenously (ml)
- Number of catheter exchange during procedure (in left atrium only)
- Are diuretics given
- What is the subject's heart rhythm at the beginning of procedure
- Is an esophageal monitoring/positioning utilized during the procedure
 - If yes, the monitoring method

- Whether the proximity to the phrenic nerve is evaluated prior to ablation of the right pulmonary vein
- What is the subject's predominant heart rhythm at the end of procedure
- If NOT in sinus rhythm, is cardioversion performed
 - Post-cardioversion rhythm
- Device use
- Number of Multi-electrode Circular IRE Catheters (D-1412-01-SI) used

3.1.10 Pulmonary vein target information during the index ablation procedure

Pulmonary vein target information during the index ablation procedure will be summarized descriptively based on RI AT, FAS, and SS AT, and the summary will be performed as follows:

- Number of valid generator applications
- Valid application locations (ostial, antral)
- Ablation status
- Pulmonary vein isolation
- Observation results
- Is adenosine and/or isoprenaline used to provoke AF prior to verification of entrance block
- Final entrance block
 - If yes, confirmed device

Index ablation procedure targets will be listed by subject. One record is prepared for each patient, including number of applications per PV, PV isolation, and whether conduction block achieved.

3.1.11 Ablation of non-PV triggers and substrate modification

The information on ablation of non-PV AF triggers and substrate modification from the subject's index ablation procedure will be summarized based on RI AT, FAS, and SS AT, including:

- Are any non-PV triggers or substrate modification targets ablated
- Other ablation targets
- Catheter type

- Generator type
- Trigger induced
- Observation results
- Bi-directional block

3.1.12 Compliance with ECG examination and 24-hour Holter monitor

The compliance of subjects with ECG examination and 24-hour Holter monitor at the 3-month, 6-month and 12-month follow-ups after the procedure will be summarized based on RI AT, FAS, and SS AT.

- Number of subjects completing the ECG examination (%)
- Number of subjects completing the 24-hour Holter monitor (%)

3.2 Effectiveness analysis

3.2.1 Effectiveness analysis

The primary effectiveness endpoint is long-term effectiveness. See section “4.1 Interim analysis” for the interim analysis performed for this endpoint. If the interim results meet the early effectiveness success criteria, the interim results will be used for new product registration. The study will continue, and descriptive analyses will be performed at the time of final analysis of the study. If the interim results do not meet the early effectiveness success criteria, the study team will remain blinded to the summary results of primary endpoint of the study, and final analysis, also as the primary analysis, will be performed in the FAS when all non-roll-in subjects undergoing ablation power have completed their 12-month follow-up visit.

3.2.1.1 Primary analysis of final analysis

The effectiveness endpoint is a composite endpoint. All occurrences of the composite events, the earliest occurrence of the composite events will be summarized for each subject. Composite events (refer to the definition of primary endpoint) include:

- a) Failure to achieve acute procedural success.
- b) Greater (>) than 1 repeat ablation for AF, AT, and AFL of unknown origin in the blanking period or any repeat ablation or surgical treatment for AF, AT, and AFL of unknown origin during the effectiveness evaluation period.
- c) Non-study catheter failure, including:
 - Use of a non-study catheter (NSC) to treat pulmonary vein targets to achieve isolation of clinically relevant PVs

and/or to ablate left atrial non-PV AF targets during the index procedure

- Use of a NSC to treat pulmonary vein targets to achieve isolation of clinically relevant PVs during repeat procedure in the blanking period
- d) Direct current or pharmacological cardioversion for AF, AT, and AFL of unknown origin during the effectiveness evaluation period.
- e) Continuous AF, AT, and AFL of unknown origin on a standard 12-lead ECG during the effectiveness evaluation period.
- f) A Class I and/or Class III AAD is prescribed for AF, AT, and AFL of unknown origin during effectiveness evaluation period, or end date of Class I and/or Class III AAD past day 90 post procedure.
- g) Oral amiodarone is prescribed post index ablation procedure.

CCI

3.2.1.2 CCI

CCI

CCI

CCI

3.2.2 Analysis of secondary effectiveness

All secondary endpoint analyses will be based on RI AT, FAS, and SS AT.

- Acute Procedural Success: the number and percentage of patients with acute procedural success will be calculated, and the two-sided exact 95% confidence interval (CI) will be calculated by the Clopper-Pearson method.
- Acute reconnection: the number and percentage of PVs/subjects with acute reconnection will be calculated, and the two-sided exact 95% confidence interval (CI) will be calculated by the Clopper-Pearson method.
- The number and percentage of PVs/subjects requiring touch-up with a non-study catheter among ablation procedures (including index and repeat ablation procedures); the two-sided exact 95% confidence interval (CI) will be calculated by the Clopper-

Pearson method. Wherein, repeat ablation is defined as any ablation procedure performed after the index procedure, including those recorded during scheduled and unscheduled visits.

- The number and percentage of subjects with repeat ablation procedures during the 12-month follow-up period will be summarized, and the two-sided exact 95% confidence interval will be calculated by the Clopper-Pearson method. The time of repeat ablation (during blanking period, during effectiveness assessment period) and the proportion of PVs/subjects that recovered will be presented. The types of arrhythmias treated with repeated ablation will be presented. Wherein, repeat ablation is defined as any ablation procedure performed after the index procedure, including those recorded during scheduled and unscheduled visits.

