6.5.5. Repeat Ablation Procedures

Repeat procedures may be performed at the discretion of the investigator. Repeat procedures for AF/AT/AFL of unknown origin⁺ recurrences during the blanking period (90 days post index procedure) must be conducted with the investigational device for ablating PV reconnections. More than 1 repeat procedure for AF/AT/AFL of

unknown origin⁺ during the blanking period is considered a failure mode for primary effectiveness. Procedures for CTI dependent flutter in the follow up period are not considered repeat procedures per protocol.

Repeat procedures performed after the blanking period may be managed per investigator discretion using a commercially available ablation catheter and generator. The follow-up schedule will remain based on the initial ablation procedure.

For the repeat procedures for AF/AT/AFL of unknown origin⁺, investigators must collect and provide information on location of reconnections of PVs and in case of atrial flutter recurrence, confirm if CTI dependent flutter or AFL of unknown origin.

⁺AFL of unknown origin is defined as all AFL except those CTI dependent AFL as confirmed by 12 or 15 leads ECG or entrainment maneuvers in an EP study.

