7.4. Criteria for terminating the trial based on the statistical reasons and justification

The interim analysis for study early termination is not planned, so this section is not applicable.

7.5. Statistical method of all data, together with the handling method of missing, unused and wrong data (including discontinuation and withdrawal) and unreasonable data

Analysis of demographic characteristics, baseline data and operation information

[figure not shown]
Demographics, baseline characteristics and procedural information will be

analyzed in the full analysis set (FAS) and the safety analysis set.

[figure not shown]
The descriptive statistics of continuous variables will include the number of subjects with valid data, number of missing, mean, standard deviation, quartiles, minimum and maximum. The descriptive statistics of categorical variables will include the frequency and percentage. The number of missing will not be included in the denominator for percentage calculation.

The data analysis plan will be documented in detail in the Statistical Analysis Plan.

CCI

CCI

Analysis of secondary endpoints

All secondary endpoints will be analyzed on the FAS.

- Acute Procedural Success: the number and percentage of patients with acute procedural success will be calculated, and the two-sided 95% confidence

interval (CI) will be calculated by the exact (Clopper-Pearson) test method.

- Acute reconnection identified by adenosine/isoproterenol challenge among all clinically relevant targeted PVs and by subject: the number and percentage of PVs/patients with acute reconnection will be calculated, and the two-sided 95% CI will be calculated by the exact (Clopper-Pearson) test method.
- Rate of PV ablation by a non-study catheter (touch-up) among all clinically relevant targeted PVs and by subject: same statistical analysis method as acute reconnection.
- Rate of repeated ablation within the 12M FU period: same statistical analysis method as acute procedural success.

The secondary endpoints will not be used for statistical inference, but for descriptive purposes. Therefore, multiplicity will not be adjusted.

Analysis of safety endpoints

The safety endpoints will be analyzed in the safety set.

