1.2.2 Secondary effectiveness endpoints

Secondary effectiveness endpoints include:

- Acute Procedural Success defined as confirmation of entrance block in all clinically relevant targeted PVs after adenosine/isoproterenol challenge. Touching up with focal catheter will be considered as acute procedural failure.
- Acute reconnection identified by adenosine/isoproterenol challenge among all clinically relevant targeted PVs and by subject.
- Rate of PV ablation by a non-study catheter (touch-up) among all clinically relevant targeted PVs and by subject.
- Rate of repeat ablation within the 12M FU period, including timing (blanking period or after blanking) and rate of PV reconnection.

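### The SAP's touch-up rate spans index and all repeat procedures, so as worded it can count a late redo with a commercial catheter as a touch-up

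*SAP*

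**What the plan says.** SAP 1.2.2 lists the secondary endpoint as "Rate of PV ablation by a non-study catheter (touch-up) among all clinically relevant targeted PVs and by subject"; Protocol 6.1.5.1 lists it in the same way. For its analysis, SAP 3.2.2 counts the veins and subjects "requiring touch-up with a non-study catheter among ablation procedures (including index and repeat ablation procedures"), with exact 95% intervals. The same bullet adds that "repeat ablation is defined as any ablation procedure performed after the index procedure". It sets no limit on period or catheter.

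Protocol 6.5.5 has two catheter rules for repeats. Those for recurrence in the blanking period "must be conducted with the investigational device for ablating PV reconnections". For later ones, "Repeat procedures performed after the blanking period may be managed per investigator discretion using a commercially available ablation catheter and generator".

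Two other places bear on the scope. Primary failure mode c), in SAP 1.2.1 and 3.2.1.1, covers non-study catheter use at the index procedure and, for repeats, only "Use of a NSC to treat pulmonary vein targets to achieve isolation of clinically relevant PVs during repeat procedure in the blanking period". Protocol 7.5 gives the touch-up rate the "same statistical analysis method as acute reconnection" and does not mention repeat procedures, so the pooling appears only in the SAP.

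**The concern.** A touch-up rate is naturally read as showing how often the study catheter could not complete isolation unaided. Neither document states that purpose, but both treat touching up with a focal catheter as failure of acute procedural success, which is judged at the end of the procedure. A redo at month 8 with a commercial catheter is treatment of a late recurrence. If it enters the touch-up count, the rate mixes acute catheter performance with late recurrence and with a catheter choice that the protocol leaves open.

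The rate could then rise with no change in what the study catheter did. A subject could be an acute procedural success and also a touch-up subject. The same redo would be reported again in the next bullet of SAP 3.2.2, which covers repeat ablation, its timing and PV recovery.

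**Working it through.** **Tracing one subject through the text.** Take a subject whose veins are all isolated by the study catheter at index and who has a PV redo with a commercial catheter at month 8.

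1. Month 8 is after day 90, so Protocol 6.5.5 permits the commercial catheter.
2. The redo is a repeat ablation under SAP 3.2.2, because it follows the index procedure.
3. It is PV ablation by a non-study catheter, which the label in SAP 1.2.2 calls touch-up.
4. On that label, the subject and each re-ablated vein enter the touch-up numerator.
5. Under failure mode c) the same redo is not a non-study catheter failure, because it lies outside the blanking period. It fails the primary endpoint only under mode b), as a repeat in the effectiveness evaluation period.

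**Denominators.** The documents state no touch-up or redo rate, so there is no figure of that kind to reproduce. I use the planned sizes in SAP 1.3.3:

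- Evaluable: n = (1.960 + 0.842)² × 0.63 × 0.37 / 0.13² = 108.3, so 109, against 110 stated.
- Enrolled: 110 / 0.90 = 122.2, so 123, as stated.

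**Shift per subject.** Each subject with a late commercial-catheter PV redo and no earlier touch-up adds 1/123 = 0.81 or 1/110 = 0.91 percentage points to the by-subject rate.

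**Illustration by subject.** All counts are assumed: 2 index touch-ups, plus the late redos shown, in other subjects. Clopper-Pearson limits are the 2.5% quantile of Beta(x, N − x + 1) and the 97.5% quantile of Beta(x + 1, N − x).

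| N | Late redos | x/N | Rate | 95% CI |
|---|---|---|---|---|
| 123 | 0 | 2/123 | 1.6% | 0.2 to 5.8 |
| 123 | 6 | 8/123 | 6.5% | 2.8 to 12.4 |
| 123 | 12 | 14/123 | 11.4% | 6.4 to 18.4 |
| 123 | 18 | 20/123 | 16.3% | 10.2 to 24.0 |
| 110 | 0 | 2/110 | 1.8% | 0.2 to 6.4 |
| 110 | 6 | 8/110 | 7.3% | 3.2 to 13.8 |
| 110 | 11 | 13/110 | 11.8% | 6.4 to 19.4 |

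**Illustration by vein.** Further assumptions: N = 110, four veins per subject, one vein per index touch-up and two veins per redo. Index only gives 2/440 = 0.45%. With six redos the numerator is 2 + 12 = 14. That gives 14/440 = 3.18% if each vein is counted once, or 14/452 = 3.10% if re-treated veins are added to the denominator. SAP 3.2.2 does not say which denominator applies.

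**A side effect on the procedure base.** Protocol 6.5.5 says that "Procedures for CTI dependent flutter in the follow up period are not considered repeat procedures per protocol", whereas the SAP's definition takes in any later ablation. This matters more for the repeat-ablation rate than for the PV touch-up count.

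**The case against.** The strongest reply is that SAP 3.2.2 speaks of veins and subjects that require touch-up, not of any use of a non-study catheter. Both documents use touching up in a within-procedure sense when they define acute procedural success. On that reading a touch-up is a non-study catheter finishing what the study catheter began, at index or at a repeat, and a redo done wholly with a commercial catheter does not count. This stands as a possible reading. A reader might infer that every late redo is certainly counted, but the documents do not settle that. Neither visible text states the narrow meaning, however, and the endpoint label points the other way. The wording needs correcting on either reading. Blacked-out sections could hold a further definition, but the SAP 3.2.2 bullet is visible in full.

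A reader might also infer that the pooling leaves device performance uninterpretable. It does not. Acute procedural success has its own exact interval, failure mode c) separates index from blanking-period repeats, SAP 3.1.10 summarises index isolation and entrance block, and SAP 2.3.4 lists all collected data. Much of the index information can be recovered.

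Nor does the point threaten the trial's conclusion. Protocol 7.5 makes the secondary endpoints descriptive, and the bias cannot flatter the device. Overlap with the repeat-ablation endpoint is not in itself an error, since descriptive endpoints here overlap elsewhere too. Finally, Protocol 6.5.5 permits a commercial catheter after blanking without requiring one, so only some late redos could count.

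**Conclusion.** The point holds as a defect of scope in one secondary line. As worded, SAP 3.2.2 can count a late PV redo with a commercial catheter as a touch-up, although the study catheter achieved full isolation at index. That scope is wider than failure mode c), and it biases the rate against the device. The primary test, its significance level and the sample size are untouched.

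The direction is clear but the size is not. The firm figure is 0.8 to 0.9 percentage points per affected subject at N = 123 or 110. The larger shifts in the table rest on assumed counts and on every listed redo treating a PV with a non-study catheter in a subject without an earlier touch-up. The two values of N are planned sizes, not the RI AT, FAS and SS AT sets on which SAP 3.2.2 will report.

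**What to change.** In SAP 3.2.2:

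- Report the touch-up rate, by PV and by subject, for the index procedure, and state both denominators.
- Show blanking-period repeats as a separate line, to match failure mode c).
- Exclude post-blanking repeats from touch-up and report them under the repeat-ablation endpoint, with catheter type if the CRF records it.

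The cost is SAP wording and one table shell, before database lock. The split by timing needs only procedure dates. A reader might infer that catheter type at late repeats is already available, but the documents do not show this. Protocol 6.5.4 lists non-study catheter use among the data of the study ablation procedure. For repeats, Protocol 6.5.5 asks for reconnection sites and flutter type. The CRF should be checked before that tabulation is promised. The change concerns reporting only and leaves the protocol's catheter rules as they are.

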6.2. Study Schedule

Schedule of Assessments

Table 2. The schedule of assessment of the study

Assessments	Pre-procedure	Procedure	Pre-Discharge	Follow-up					
				7 Day	1 Month	3 Month	6 Month	12 Month	(UNS)
Visit	Screening/ Baseline	D0	D/C	D7 D7-10	D30 D23-37	D90 D76-104	D180 D150-210	D365 D335-395	
Clinic visit	●		●	(●) ¹	(●) ¹	●	●	●	●
Patient Informed Consent ²	●								
Inc&Excl Criteria	●								
Demographics	●								
Physical Exam	●		●		(●) ¹	●	●	●	●
Medical History ³	●								
Pregnancy test ⁴	●								
LA and LVEF assessment ⁵	●								
LA thrombus detection ⁶	●	●							

Assessments	Pre-procedure	Procedure	Pre-Discharge	Follow-up					
				7 Day	1 Month	3 Month	6 Month	12 Month	(UNS)
Ablation Assessments		●							
Device Deficiencies		●							
TTE ⁷			●						
Concomitant medication ⁸	●	●	●	●	●	●	●	●	●
(Repeat ablation) ⁹				(●)	(●)	(●)	(●)	(●)	(●)
AF/AT/AFL recurrence			●	●	●	●	●	●	●
12 or 15 leads ECG	(●) ¹⁰		●			●	●	●	(●) ¹⁰
24-hour Holter						●	●	●	
Adverse Events ¹¹	●	●	●	●	●	●	●	●	●
Completion/discontinuation form ¹²		(●)	(●)	(●)	(●)	(●)	(●)	●	

¹ Telephone/virtual or clinic visit.

² Procedure must be done within 90 days of consent.

³ Medical history should include but not be limited to vital signs, arrhythmia, AAD therapy failure, NYHA, CHA2DS2-VASc score, thromboembolic events and other heart diseases.

⁴ In all women of childbearing age and potential (within 2 years after menopause). To be completed within 72-hours prior to ablation procedure.

⁵ Imaging should be done within 6 months prior to enrollment

⁶ Performed within 48 hours of the ablation procedure to rule out the presence of atrial thrombus using one of the following modalities TEE, ICE, CT (TEE intolerance).

⁷ All subjects will undergo TTE prior to discharge to evaluate pericardial effusion

⁸ Concomitant medication: only cardiac (i.e. anti-arrhythmia drugs, PPI, anticoagulation regimen) & index procedure related (i.e. adenosine, pain medication) & AE treatment

⁹ Repeat ablation: any ablation procedure performed after the index procedure; data will be recorded at follow-up as well as at any unscheduled visits.

¹⁰ Standard of care 12 or 15 leads ECG will be collected if available.

¹¹ Aes must be collected from the time the subject signs the informed consent onward.

¹² 12-month visit/ last completed visit or last data collection

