- AF/AT/AFL recurrences: for subjects with AFL recurrence identified through Holter monitoring, a 12 or 15 leads ECG MUST be collected.
- Medication: Cardiac and Anti-coagulation medication regimen, AE related
- Repeat ablation: any ablation procedure performed after the index procedure will be recorded at 3-, 6- and 12-month follow-up as well as at any unscheduled visits.
- Cardiac related hospitalization and cardioversions

- Subject completion/ discontinuation form (12-month)

Early Termination Visit

If early termination of the study is required due to safety concerns, each site will undergo a monitoring visit to conclude any outstanding issues, collect all outstanding CRF information, verify device accountability, and discuss any other items relevant to the conclusion of the study. Any enrolled subjects will continue to be followed per the study protocol requirements. In case of early termination due to safety concerns, reporting to EC and CA may be required per local regulations.

Unscheduled Visit

If a subject returns for a potential study related cardiovascular or neurological visit outside of the protocol-defined visit schedule provided in table 2, the visit will be considered “unscheduled” (UNS). An investigator may request an unscheduled visit in the presence of a new or worsened cardiovascular condition or neurological deficit. If the unscheduled visit is for a repeat ablation procedure, the protocol follow-up schedule is based on the index ablation procedure. For all unscheduled visits, an unscheduled visit eCRF must be completed and the subject must also return for their next scheduled study visit per clinical investigational plan.

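### SAP 3.2.2 counts every later ablation as a repeat ablation, although protocol 6.5.5 says procedures for CTI-dependent flutter are not repeats

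*SAP*

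**What the plan says.** Protocol 6.5.5 (Repeat Ablation Procedures) sets a boundary on the term: "Procedures for CTI dependent flutter in the follow up period are not considered repeat procedures per protocol".

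SAP 3.2.2 (Analysis of secondary effectiveness) sets none. Its repeat-ablation bullet begins "The number and percentage of subjects with repeat ablation procedures during the 12-month follow-up period will be summarized", attaches a two-sided exact 95% Clopper-Pearson interval, and then defines the term: "Wherein, repeat ablation is defined as any ablation procedure performed after the index procedure, including those recorded during scheduled and unscheduled visits". The same bullet plans the timing of repeats, the proportion of veins and subjects with recovered conduction, and this display: "The types of arrhythmias treated with repeated ablation will be presented".

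The endpoint itself, in SAP 1.2.2, carries no arrhythmia qualifier: "Rate of repeat ablation within the 12M FU period, including timing (blanking period or after blanking) and rate of PV reconnection".

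Two other protocol passages use the broad wording. Footnote 9 to the schedule in section 6.2 reads "Repeat ablation: any ablation procedure performed after the index procedure; data will be recorded at follow-up as well as at any unscheduled visits", and section 6.5.6 says that "any ablation procedure performed after the index procedure will be recorded at 3-, 6- and 12-month follow-up".

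Protocol 7.5 makes the secondary endpoints descriptive, with no inference and no multiplicity adjustment.

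**The concern.** One term has two meanings, and the meaning fixes the numerator of a named secondary effectiveness endpoint. A subject who returns only for ablation of CTI-dependent flutter has not had a repeat procedure under protocol 6.5.5, but is a repeat-ablation subject under SAP 3.2.2.

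At stake is how the 12-month rate and its interval are read. Someone who takes the term from the protocol would read the reported figure as excluding CTI-dependent flutter, when it may not. The recovery figure in the same bullet is exposed too. Protocol 6.5.5 requires the location of vein reconnections only for repeats for AF, AT or AFL of unknown origin, so the SAP's wider set can contain procedures for which no such data are required.

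**Working it through.** **Step 1: the passages side by side.**

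| Place | Role of the passage | CTI-dependent flutter procedure in follow-up |
|---|---|---|
| Protocol 6.5.5 | Rule on repeat procedures | Not a repeat |
| Protocol 6.2, footnote 9 | Note to the visit schedule | Included (any later ablation) |
| Protocol 6.5.6 | List of follow-up assessments | Included (any later ablation) |
| SAP 1.2.2 | Endpoint wording | Silent |
| SAP 3.2.2 | Analysis definition, with interval | Included (any later ablation) |

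The two schedule passages concern what is recorded, and capturing every later ablation is compatible with a narrower protocol meaning of a repeat. SAP 3.2.2 cannot be read that way, because it defines what is counted. The clear conflict is protocol 6.5.5 against SAP 3.2.2.

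**Step 2: is it resolved elsewhere?** The SAP introduction says the plan is based on protocol version 2.2. SAP section 5 lists two new analysis sets and the removal of one adverse-event analysis, and does not mention this definition. Parts of the SAP are redacted, so this covers visible text only.

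**Step 3: which subjects are affected?** The count is by subject.

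- Later ablation only for AF, AT or AFL of unknown origin: counted under both rules.
- Both that and a CTI-dependent flutter procedure: counted once under both rules.
- Only a CTI-dependent flutter procedure: counted under SAP 3.2.2 only.

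Let *x* be the number of subjects counted under 6.5.5, *c* the number in the third group and *n* the denominator. The rates are *x/n* and *(x + c)/n*, and the difference is *c/n*, which is never negative.

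**Step 4: size.** The sizes of the three analysis sets used (RI AT, FAS, SS AT) are not given. I take *n* = 110, the evaluable target in SAP 1.3.3, and *n* = 123, the planned non-roll-in enrolment.

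- 1/110 = 0.91 percentage points per such subject
- 1/123 = 0.81 percentage points per such subject

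**Step 5: illustration with the interval.** The documents give no repeat-ablation or CTI-flutter rate, so every count below is an assumption. For *k* subjects counted out of *n*, the Clopper-Pearson limits are the 0.025 quantile of Beta(*k*, *n* − *k* + 1) and the 0.975 quantile of Beta(*k* + 1, *n* − *k*). At *n* = 110:

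| *x* | *c* = 0 | *c* = 1 | *c* = 3 |
|---|---|---|---|
| 4 | 3.6% (1.0–9.0) | 4.5% (1.5–10.3) | 6.4% (2.6–12.7) |
| 8 | 7.3% (3.2–13.8) | 8.2% (3.8–15.0) | 10.0% (5.1–17.2) |
| 12 | 10.9% (5.8–18.3) | 11.8% (6.4–19.4) | 13.6% (7.8–21.5) |

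At *n* = 123, going from 8 to 11 subjects moves the rate from 6.5% (2.8–12.4) to 8.9% (4.5–15.4).

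**Step 6: the primary endpoint.** Component (b) names its own arrhythmias. After blanking it counts "any repeat ablation or surgical treatment for AF, AT, and AFL of unknown origin during the effectiveness evaluation period", and its blanking-period clause is limited in the same way. CTI-dependent flutter procedures do not enter it under either definition.

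**The case against.** The strongest reply is that the SAP is not ambiguous. It states one rule, the rule fits an endpoint with no arrhythmia qualifier, and a programmer can follow it. The arrhythmia types will be displayed, so CTI procedures would be visible. The count can only move against the device, and the endpoint is descriptive.

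All of that stands, and it keeps the point small. It does not remove the conflict: a clear rule can still contradict the protocol on which it is based, and the arrhythmia display supplies no subject-level rate or interval on the 6.5.5 meaning.

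Three stronger readings are tempting, and the documents do not support them.

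- A reader might infer that the protocol plainly contradicts itself. Footnote 9 and section 6.5.6 do use the broad wording, but both can be read as recording instructions that coexist with 6.5.5.
- A reader might infer that the secondary rate must match primary component (b). Nothing requires this. Component (b) has its own rules, including a threshold of more than one repeat during blanking and the inclusion of surgical treatment.
- A reader might infer that the touch-up bullet in SAP 3.2.2, which pools index and repeat procedures, is also in error. No passage contradicts that pooling.

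**Conclusion.** The conflict between protocol 6.5.5 and SAP 3.2.2 is real, and no visible text reconciles it. It affects the 12-month repeat-ablation rate, its interval, and the set used for vein recovery.

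The effect is about 0.9 points per CTI-only subject at an assumed *n* of 110 and 0.8 at 123. It is zero if there are none, and for the repeat-ablation rate it is always upward. The direction for the recovery proportion cannot be told from the documents. The intervals shown rest on assumed counts and indicate scale only.

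The primary endpoint, its test and the sample size are not affected. This should be corrected because the rule as written contradicts the protocol and the remedy is cheap; it is not a threat to the trial's main conclusion.

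**What to change.** Before database lock, reconcile SAP 3.2.2 with protocol 6.5.5 by adding a sentence to SAP 3.2.2 that says which definition governs the endpoint. Then report two labelled figures:

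- the repeat-ablation rate with its Clopper-Pearson interval, excluding CTI-dependent flutter procedures in line with 6.5.5;
- beside it, the any-ablation rate.

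The recovery figure should state which of the two sets it uses.

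The cost is one sentence and a filter on arrhythmia type. The filter should rest on the arrhythmia type that SAP 3.2.2 already plans to present. The duty in protocol 6.5.5 to confirm whether recurrent flutter is CTI dependent is weaker support, because it is attached to repeats for AF, AT or AFL of unknown origin. Settling the definition before lock also avoids choosing it once the counts are known.
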